#### **Background and Aim**

This statistical analysis plan concerns the long-term follow-up (4-2.5 years after baseline assessment) of the VIA Family trial. We conducted the VIA Family trial in Denmark between 2017-2020. The trial aimed to test for superiority of the VIA Family intervention compared with treatment as usual (TAU) in improving children's, parents' and families' functioning and wellbeing. Eligible families had at least one parent with a lifetime severe mental illness diagnosis (SMI) (i.e. recurrent moderate to severe depression, bipolar disorder, or schizophrenia spectrum disorder), at least one child between the age of 6-12 years, and lived within the municipalities of Frederiksberg or Copenhagen (Denmark). The trial had a randomized, two-armed, parallel and controlled design. The participating families were randomly allocated to both groups with an allocation ratio of 1:1. For more information see study protocol.

We invited families for the 4-year follow-up assessment who at baseline had been randomized to one of the two treatment arms. Families who had withdrawn their consent for participation or had requested not to be

contacted for future follow-up were not invited for participation. At 4-year follow-up we invited only one parent to participate to represent the primary informant of the child.

The aim of the 4-year follow-up was to study potential long-term effects of the VIA Family intervention.

## Methods and Measures

Measurements for the 4-year follow-up study were:

Children's Global Assessment Scale (CGAS)

Strengths and Difficulties Questionnaire (SDQ)

Health-Related Quality of Life Questionnaire: KIDSCREEN

This is Me (TIM)

Home Observation Measurement of the Environment (HOME)

Family Assessment Device (FAD)

Parental Stress Scale (PSS)

Personal and Social Performance Scale (PSP)

Parenting Scale (PS)

## Hypotheses

We expect that the experimental intervention VIA Family has positively impacted long term improvements in parenting, home environment, parent- and family functioning and other parental and family-related factors of protection for their children. We therefore expect that we will observe greater improvements in child functioning (CGAS), less signs of mental health (SDQ), improved child quality of life (KIDSCREEN) and improved self-esteem (TIM) at 4-years follow-up, along improvements in parent and family related outcomes (PS, PSS, HOME, FAD, PSP) in families allocated to VIA Family compared with TAU.

The primary hypothesis is:

- The VIA Family intervention will demonstrate a superior change in SDQ from baseline (timepoint 0) to 4-year follow-up (timepoint 2) compared with TAU.

The secondary hypotheses are:

- The VIA Family intervention will demonstrate superior change in CGAS, KIDSSCREEN, TIM, HOME, FAD, PSS, PS, and PSP, respectively from baseline (timepoint 0) to 4-year follow-up (timepoint 2) compared with TAU.

### Statistical Analyses

All analyses will be performed in the intention-to-treat (ITT) population including study participants as randomized regardless of treatment adherence and dropout status. The analyses will be conducted using the statistical software R^11 after the last participant completes the follow-up assessment and after the formulation of the statistical analysis plan. A two-tailed p-value of < 5% will be considered statistically significant.

### Descriptive statistics

Baseline clinical and sociodemographic characteristics of children, parents, and families will be reported according to allocation group and drop-out status (see Table 1).

Table 1

Variables	Instrument	Treatment As Usual		VIA Family		All
Drop-out status at 4 years follow up		participating	dropout	participating	dropout	
Children's characteristics	n(%)					
Biological sex, female participants a	n (%)					
Age at baseline a	mean (SD)					
Global functioning a	CGAS, mean (SD)					
Any Current Diagnosis 1,a	K-SADS-PL, n (%)					
Dimensional psychopathology	CBCL total problem score, T-score (Danish norms), mean (SD)					
High ( $\geq 15\%$ ) absence from school	Data from municipalities or schools, n (%)					
Neurocognition						
Estimate of general intelligence	RIST, scaled scores, mean (SD)					
Processing speed	WISC-IV coding , scaled scores (Danish norms), mean (SD)					
Visual Memory	RCFT immediate recall, T-scores (US norms), mean (SD)					
Verbal Memory – immediate	Memory for Stories, immediate recall (TOMAL-2), scaled scores (US norms), mean (SD)					
Verbal Memory- delayed	Memory for Stories, delayed recall (TOMAL-2) scaled scores (US norms), mean (SD)					
General Executive Functioning	BRIEF, T-score (Danish norms), mean (SD)					
Social responsiveness	SRS-2, raw score, mean (SD)					

Family and home characteristics	n					
Quality of home environment 2,a	MC-HOME/EA-HOME, mean (SD)					
Single parent family 	parent-reported , n (%)					
Having two parents with SMI or/and substance misuse lifetime  diagnoses (solely out of families with two caregivers)	SCAN interview / patient journal, n (%)					
Index parent's diagnosis	n					
Lifetime  SZ a	SCAN interview / patient journal, n (%)					
Lifetime  BP a	SCAN interview / patient journal, n (%)					
Lifetime  rMDD a	SCAN interview / patient journal, n (%)					
Index parent with comorbid diagnosis 	SCAN interview / patient journal, n (%)					
Primary caregiver's characteristics	n					
SMI or/and substance misuse lifetime  diagnoses	SCAN interview / patient journal, n (%)					
General functioning (higher score better functioning)	PSP, mean (SD)					
Parental Stress (higher score more stress)	PSS, mean (SD)					
Family functioning (lower score better functioning)	FAD, mean (SD)					
Employment status parents						
Currently employed or studying 	Interview , n (%)					
Educational level parents						
Primary/lower secondary	n (%)					
Upper secondary, vocational, or short-cycle tertiary	n (%)					
Bachelor's degree, equivalent, or higher	n (%)					
Support at baseline (family)	n					
Family receiving support from municipalities/MHS six months prior to baseline 	Interview / Data from municipalities, n (%)					

1 Current Diagnosis within the last 8 weeks, excl. Elimination Disorder, Simple Phobia, Tics/Tourette's Syndrome  
 2 For children living 50/50 with mother and father, the HOME interview was done in both homes  
 3 Child has only one caregiver  
 4 During child's life (including the prenatal period)  
 5 Personality disorder, substance abuse, ADHD, PTSD, or eating disorder  
 6 Any form of employment, no minimum working hours, absence from work due to e.g., illness or maternity leave included as work  
 ADHD-RS Attention Deficit Hyperactivity Disorder Rating Scale; BRIEF Behavior Rating Inventory of Executive Function; CALS Children's Affective Liability Scale; CBCL Child Behavior Checklist; CGAS Children's Global Assessment Scale; CTS Childhood Trauma Screener; FAD Family Assessment Device, HOME Home Observation for Measurement of the Environment; K-SADS-PL Kiddie Schedule for Affective Disorders and Schizophrenia - Present and Lifetime; PSP Personal and Social performance Scale; PSS Parental Stress Scale; RCFT Rey Complex Figure Test; RIST Reynolds Intellectual Screening Test; SCAN Schedules for Clinical Assessment in Neuropsychiatry; SRS-2 Social Responsiveness Scale- Version 2; TOMAL-II Test of Memory and Learning, 2nd Edition; WISC-IV Wechsler Intelligence Scale for Children, 4th Edition

**Primary and secondary analyses** Changes in child-specific outcomes (CGAS, SDQ, KIDSSCREEN, TIM, HOME, PS) will be analyzed using a linear mixed model including allocation group, baseline measurement, child age,

and sex (registered at birth) as fixed effects and a random effect of family to address non-independence among siblings within the same family.

Changes in parent- and family-specific outcomes (FAD, PSP, PSS) including allocation group, baseline measurement, and parental diagnosis as covariates.

Mean differences in change between the VIA Family intervention and TAU groups, along with a 95% confidence interval, will be reported with corresponding p-values.

Model assumptions will be assessed using residual diagnostics. Severely skewed outcomes will be log-transformed prior to analysis.

### Handling of missing data

Characteristics of dropouts and completers will be compared between the allocation groups in descriptive tables to identify any possible systematic patterns or reasons for participant discontinuation. Reasons for dropout will be reported.

Missing data in the primary and secondary analyses will be handled by standard multiple imputations using the mice-package and Amelia-package in R. Missing values in each treatment arm separately will be imputed 100-fold including the variables specified in Table 2 below. Convergence will be assessed by traceplots.

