**Table 2: Variables for imputation on missing data.**

*Unless specified otherwise, data from baseline, 18 months follow-up, and 50 months follow-up will be included.*

Child	Parent/family	Teacher
Covariates	Covariates	
Age a	Age a	
Sex at birth a	Parental SMI diagnosis a	
Out-of-home placement b,c	Parents living together	
Clinician-rated interview	Clinician rated interview	Surveys about the child
CGAS score	PSP, Index parent, total score	TRF, total score a,b
KSADS, any diagnoses (binary: yes/no) a,b	PSP, other parent, total score	BRIEF, total score a,b
	HOME , total score	SRS, total score a
Cognitive tests	Surveys about the child	
RIST – total score a	CBCL, total score a,b	
TOMAL-II total score a	BRIEF, total score a,b	
Coding (WISC) total score a	SRS, total score a	
RCFT - total score a	SDQ, total score	
Self-report questionnaires	Self-report questionnaires	
This Is Me, total score	PSS Index, total score	
KIDSCREEN, total score	PSS, other parent, total score	
a Baseline data		

b 18 months follow up data (end-of-intervention)			
c 50 months follow up data			

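### Table 2, the list of imputation variables, omits two secondary outcomes (FAD and PS) at every visit; a smaller gap is that the imputation states no family term

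*SAP*

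**What the plan says.** Hypotheses makes SDQ the primary outcome and names eight secondary outcomes, for which it expects "superior change in CGAS, KIDSSCREEN, TIM, HOME, FAD, PSS, PS, and PSP, respectively from baseline" to the 4-year follow-up. FAD and PS are among the eight.

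Primary and secondary analyses places PS with the child-specific outcomes. These are modelled with allocation, baseline measurement, child age, sex and a random family effect. FAD is placed with the parent- and family-specific outcomes, modelled with allocation, baseline measurement and parental diagnosis. Both outcomes are therefore adjusted for their own baseline.

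On missing values, Handling of missing data says: "Missing data in the primary and secondary analyses will be handled by standard multiple imputations using the mice-package" (Amelia is named as well), and then: "Missing values in each treatment arm separately will be imputed 100-fold including the variables specified in Table 2 below". The note above Table 2 sets the visits: "Unless specified otherwise, data from baseline, 18 months follow-up, and 50 months follow-up will be included". Table 2 has rows for CGAS, SDQ, KIDSCREEN, This Is Me, HOME, PSP and PSS, together with covariates and auxiliary measures. It has no row for FAD or PS and no family identifier or cluster term.

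Statistical Analyses adds: "All analyses will be performed in the intention-to-treat (ITT) population including study participants as randomized regardless of treatment adherence and dropout status".

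**The concern.** The SAP chose to list its imputation variables, and the list does not cover its own outcomes. An analyst who follows it has two options for FAD and PS.

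- **Leave them unimputed.** Every participant without a 4-year score then drops out of an analysis declared to be intention-to-treat, and the statement that the secondary analyses are imputed is not met.
- **Impute them from Table 2 alone.** The imputation model then lacks a covariate that the analysis model uses, normally the strongest single predictor of the missing score. Precision is lost. If dropout depends on baseline in one arm but not the other, the imputed scores in that arm are pulled toward the completers and the group difference is biased. If TAU dropouts start worse, the bias works against VIA Family; if VIA Family dropouts start worse, it works in its favour.

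A smaller mismatch concerns siblings. Families were randomised, and the child models allow for correlation within a family. An imputation without a family term makes imputed siblings alike only through shared predictors, which can make the interval for a child outcome too narrow.

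**Working it through.** **1. Outcomes against Table 2.** This step needs no assumption.

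| Outcome | Role | Own baseline in analysis model | In Table 2 |
|---|---|---|---|
| SDQ | primary | yes | yes |
| CGAS, KIDSCREEN, TIM, HOME, PSP, PSS | secondary | yes | yes |
| FAD | secondary | yes | no |
| PS | secondary | yes | no |

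Coverage is 7 of 9 outcomes, or 6 of 8 secondary outcomes. FAD was measured at baseline, since Table 1 reports it. No redaction or visible break in the extracted table explains the gap.

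**2. Size for a family-level outcome such as FAD.** The SAP gives no sample size, correlation or dropout figure, so every input here is assumed: 45 families per arm; dropout d = 0.35; baseline to 4-year correlation 0.6; and the Table 2 variables summarised by one score correlated r with both baseline and outcome. TAU dropout depends on baseline, with a dropout-to-completer gap of g SD. Dropout in the other arm is random.

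The true outcome gap of TAU dropouts is about 0.6 × g. Imputed from the summary score alone, it is about r × r × g. The bias of the group difference is therefore about d × g × (0.6 − r²).

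- g = 0.48: 0.35 × 0.48 = 0.168. Multiplied by 0.51 / 0.35 / 0.11 for r = 0.3 / 0.5 / 0.7, this gives 0.086 / 0.059 / 0.018 SD.
- g = 0.77: 0.35 × 0.77 = 0.2695, giving 0.137 / 0.094 / 0.030 SD.
- g = 0: nil.

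A simulation with the same inputs agrees (4000 replicates, 20 imputations, null effect, imputation within arm, outcome regressed on allocation and baseline, Rubin's rules). Monte Carlo error of the bias is 0.003 to 0.004 SD.

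| | r = 0.3 | r = 0.5 | r = 0.7 |
|---|---|---|---|
| Bias without own baseline, g = 0.48 | 0.082 | 0.064 | 0.018 |
| Bias without own baseline, g about 0.77 | 0.136 | 0.096 | 0.034 |
| SE without own baseline, random dropout | 0.254 | 0.241 | 0.216 |
| SE with own baseline, random dropout | 0.222 | 0.220 | 0.212 |

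The SE ratios are 0.254/0.222 = 1.14, 0.241/0.220 = 1.10 and 0.216/0.212 = 1.02. With own baseline in the imputation, bias is at most 0.006 SD. Rejection rates at the SAP's two-sided 5% level were 2.7–6.0% without own baseline and 3.7–4.9% with it, so the harm is bias and lost precision rather than clear type I inflation.

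Left unimputed, bias is at most 0.005 SD and the SE is 0.211–0.214, because the analysis model itself conditions on the baseline that drives dropout. About 35% of families leave the analysis under the assumed dropout.

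**3. Family term for a child outcome.** All inputs are again assumed: 45 families per arm, whole families lost, scores at 0, 18 and 50 months, one shared predictor explaining a set share of the family effect, 4000 replicates, Monte Carlo error about 0.35–0.4 points.

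| Children per family | ICC | Dropout | Share explained | Type I error | Model SE / true SE |
|---|---|---|---|---|---|
| 1.5 | 0.5 | 40% | 25% | 5.0% | 0.97 |
| 2 | 0.3 | 30% | 25% | 5.8% | 0.96 |
| 2 | 0.5 | 40% | 0 | 6.4% | 0.91 |
| 2 | 0.5 | 40% | 25% | 6.9% | 0.92 |
| 2 | 0.5 | 40% | 50% | 6.2% | 0.94 |
| 2 | 0.5 | 40% | 75% | 5.3% | 0.96 |
| 2 | 0.6 | 40% | 25% | 6.8% | 0.91 |
| 2 | 0.6 | 40% | 75% | 5.5% | 0.97 |

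Two-level imputation gave 3.8–4.5%, with SE ratios of 1.02–1.04.

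A cruder set-up (1500 replicates, two children per family, no 18-month score, no shared family predictor, analysis of family means) gave 3.8–4.3% at ICC 0, 6.2–6.9% at ICC 0.3 and 6.1–9.3% at ICC 0.5, for 20–40% of families missing. Its complete-case comparator ranged from 3.8% to 6.3%.

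**The case against.** **The word including.** It can be read as non-exhaustive, so that each outcome is imputed with its own baseline and Table 2 supplies the auxiliaries. That reading does no harm. It is hard to square with a table that names the other seven outcomes one by one, and if it is what was meant, the imputation model for these two outcomes is simply not stated. Either way the same correction is needed.

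**The harm is limited.** This stands. Two of eight secondary outcomes are affected. Leaving them unimputed costs almost nothing in the illustration beyond the conflict with the SAP's own statements. The largest bias needs a strong baseline gap in one arm only, together with weak auxiliaries.

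**There are partial safeguards.** Table 1 shows baseline FAD by arm and dropout status, and Sensitivity analyses plans further adjustment under differential dropout. These would expose the FAD pattern, but they do not put the baseline into the imputation, and Table 1 has no PS row.

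**Stronger readings that the SAP does not support.**

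- A reader might infer that the primary result is compromised by the omission. It is not: SDQ is in Table 2.
- A reader might apply the bias figures to PS. The illustration has one value per family and no age, sex or family effect, whereas the SAP analyses PS per child, so no size is given for PS.
- A reader might infer that the SAP prescribes single-level imputation. It says standard, which does not settle the matter, and Table 2 holds shared family predictors that carry some of the sibling correlation. The family term is an omission, not a contradiction.

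**Conclusion.** The omission of FAD and PS from Table 2 is established by the text alone and should be corrected. Its size is not established, because the SAP gives none of the inputs. If the two outcomes are left unimputed, the fault is mainly a conflict with the SAP's own imputation and intention-to-treat statements. If they are imputed without their own baseline, a family-level outcome such as FAD would have a standard error 2–14% larger under random dropout. It would also have a bias of nil under random dropout and about 0.02–0.14 SD when only TAU dropout depends on baseline.

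The missing family term is a minor second point, which does reach the primary SDQ analysis. In the fuller simulation, type I error is between nil and about two points above 5%. The higher figure from the cruder set-up omits predictors that Table 2 contains. The result depends on ICC, siblings per family and dropout, so it supports a clarification and not a claim about this trial's error rate.

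**What to change.** **Main.** Add FAD and PS to Table 2 at every visit at which they were collected. State that the imputation model for each outcome contains that outcome's own baseline and the covariates of its analysis model. This takes two table rows and one sentence, and needs no new data.

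**Secondary.** State that the child-specific outcomes, as listed under Primary and secondary analyses (CGAS, SDQ, KIDSCREEN, TIM, HOME and PS), are imputed within arm by a two-level method with family as the cluster. State that FAD, PSP and PSS are imputed at family or parent level. Following that list also settles HOME, which Table 2 places in its parent/family column while the analysis treats it as child-specific. The cost is some programming and possibly slightly wider intervals: the two-level method was mildly conservative in the simulation.

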**Table 2: Variables for imputation on missing data.**

*Unless specified otherwise, data from baseline, 18 months follow-up, and 50 months follow-up will be included.*

Child	Parent/family	Teacher
Covariates	Covariates	
Age a	Age a	
Sex at birth a	Parental SMI diagnosis a	
Out-of-home placement b,c	Parents living together	
Clinician-rated interview	Clinician rated interview	Surveys about the child
CGAS score	PSP, Index parent, total score	TRF, total score a,b
KSADS, any diagnoses (binary: yes/no) a,b	PSP, other parent, total score	BRIEF, total score a,b
	HOME , total score	SRS, total score a
Cognitive tests	Surveys about the child	
RIST – total score a	CBCL, total score a,b	
TOMAL-II total score a	BRIEF, total score a,b	
Coding (WISC) total score a	SRS, total score a	
RCFT - total score a	SDQ, total score	
Self-report questionnaires	Self-report questionnaires	
This Is Me, total score	PSS Index, total score	
KIDSCREEN, total score	PSS, other parent, total score	
a Baseline data		

b 18 months follow up data (end-of-intervention)			
c 50 months follow up data			

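### Table 2, the SAP's imputation list, omits two secondary outcomes (FAD and PS) with their baselines, and its PSP and PSS rows do not fit the one-parent follow-up

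*SAP*

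**What the plan says.** SAP, Handling of missing data: "Missing data in the primary and secondary analyses will be handled by standard multiple imputations using the mice-package" (and Amelia). The same section continues: "Missing values in each treatment arm separately will be imputed 100-fold including the variables specified in Table 2 below". The heading rule of Table 2 reads: "Unless specified otherwise, data from baseline, 18 months follow-up, and 50 months follow-up will be included". Superscripts restrict some rows to baseline or 18 months.

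Hypotheses names SDQ as the primary outcome and CGAS, KIDSCREEN, TIM, HOME, FAD, PSS, PS and PSP as secondary, each tested for change from baseline. Primary and secondary analyses puts the baseline value of the outcome in every model: PS in the child-level mixed model, and FAD, PSP and PSS in the parent and family model. Statistical Analyses sets an intention-to-treat population regardless of dropout.

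On the parents, Background and Aim states: "At 4-year follow-up we invited only one parent to participate to represent the primary informant of the child". Table 2 has four parent rows without a superscript: "PSP, Index parent, total score", "PSP, other parent, total score", "PSS Index, total score" and "PSS, other parent, total score". Table 1 reports baseline PSP, PSS and FAD under the primary caregiver.

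**The concern.** An imputation model should contain every variable of the analysis model it serves, above all the outcome and its baseline. For FAD and PS the only list the SAP gives contains neither. Imputing a follow-up score without its own baseline discards its likely best predictor. It also pulls the imputed scores of dropouts towards the completers' mean, even when the dropouts started from a different level. If that happens differently in the two arms, the treatment difference moves. The SAP itself allows for differential dropout (Sensitivity analyses, item d).

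The parent rows raise a smaller question. The plan takes 50-month scores from two people when one was invited, and it does not say whose PSP, PSS or FAD is the outcome, or whose score is its baseline covariate.

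**Working it through.** The SAP gives no figure to reproduce on this point. Steps 1, 2 and 4 are comparisons of its sections; step 3 uses assumed inputs, because the SAP states no counts, dropout rates or correlations.

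**1. Outcome coverage.** Hypotheses lists nine instruments. Table 2 contains SDQ, CGAS, KIDSCREEN, TIM, HOME, PSP and PSS, all without a time restriction. 9 - 7 = 2 are missing, FAD and PS, which are 2 of the 8 secondary outcomes.

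**2. What the list then implies for FAD and PS.**
- Reading A: Table 2 is complete, and FAD and PS are not imputed. The analysis is then baseline-adjusted complete cases, against the missing-data section and the intention-to-treat population.
- Reading B: follow-up FAD and PS are imputed from the Table 2 variables, but their baselines are not among them.

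**3. Size under reading B.** Let d be the dropout share in an arm, b the slope of follow-up on baseline in SD units, and g the baseline gap between that arm's dropouts and completers. Without auxiliaries, dropouts are imputed around the completers' mean, whereas their expected mean differs from it by b x g. The arm mean therefore shifts by d x b x g. Randomisation balances the full-sample baselines, so adjusting for baseline does not remove the shift. With g = 0.5 SD in one arm only:

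| d | b | Shift in group difference (SD) |
|---|---|---|
| 0.2 | 0.5 | 0.2 x 0.5 x 0.5 = 0.05 |
| 0.2 | 0.7 | 0.2 x 0.7 x 0.5 = 0.07 |
| 0.4 | 0.5 | 0.4 x 0.5 x 0.5 = 0.10 |
| 0.4 | 0.7 | 0.4 x 0.7 x 0.5 = 0.14 |

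Equal gaps in both arms cancel; opposite gaps double the shift.

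Auxiliaries reduce it. The simulation used 50 or 100 families per arm, the same d and b, and three auxiliaries correlated 0.3-0.5 with the baseline. It imputed by arm and then fitted a baseline-adjusted model. The shift was 0.02-0.11 SD with the gap in one arm, 0.03-0.22 SD with opposite gaps, and at most 0.006 SD with equal gaps. With the own baseline included, or in baseline-adjusted complete cases, bias under differential dropout stayed within 0.015 SD.

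With no link between dropout and baseline, leaving the baseline out raised the standard error by 2-10% (b = 0.5) or 9-26% (b = 0.7) against imputing with it. Against complete cases the rise was 3-40%; a narrower set of inputs (auxiliaries correlated 0.4) gave 4-20%.

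**4. Parent scores.** At 50 months Table 2 has 2 instruments x 2 parents = 4 cells per two-parent family. One invited parent fills at most 2, so at least 2/4 = 50% are empty by design. The two parents are never seen together at 50 months, so the relation between their scores then cannot be estimated. Each parent's own score can still be predicted from that parent's scores at baseline and 18 months. In simulation the effect on the standard error of a parent mean was 1-2%.

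The sections also identify the parent differently:
- Background and Aim: one invited parent, as the child's primary informant.
- Table 1: the primary caregiver, for PSP, PSS and FAD.
- Table 2: index and other parent, for PSP and PSS.
- Primary and secondary analyses: no parent named.

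Table 1 counts primary caregivers with severe mental illness or substance misuse separately from the index parent's diagnosis, so the two need not be the same person.

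**The case against.** The best defence is the word *including* in the missing-data section. It may mean that the analysis variables enter the imputation anyway and that Table 2 adds to them. FAD, PS and their baselines would then be present and no harm follows. If Table 2 is instead exhaustive, the result is baseline-adjusted complete cases, which also showed little bias in step 3. This stands as a limit on the harm: the shifts and precision losses belong to reading B alone. It does not rescue the list. Table 2 is headed as the imputation variables, no other list is given, and it names the other seven outcomes explicitly, so a reader has no ground for treating these two as implied.

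A differential pattern would also be partly visible: Table 1 reports baseline FAD by arm and dropout status. That helps for FAD, but Table 1 has no PS row.

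On the two-parent rows, the defence is largely right. The relation that cannot be estimated is not a target of any analysis, and the effect on the outcome estimates is small.

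A reader might infer that PSP and PSS are index-parent outcomes, so that every family whose other parent was seen has a missing outcome. The documents do not support this. No passage says so, and both Background and Aim and Table 1 point to the primary informant or caregiver.

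**Conclusion.** The point holds for secondary outcomes only. The imputation list is wrong for FAD and PS: taken literally it contradicts either the promise to impute all secondary analyses or the baseline-adjusted models. This should be corrected before analysis.

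A reader might go further and infer that the FAD and PS estimates will be biased. That needs three things together: imputation without the own baseline, dropout related to that baseline, and a relation that differs by arm. The SAP states none of these. Under assumed inputs the hand calculation gives 0.05-0.14 SD for a gap in one arm before auxiliaries. The larger simulated shifts need opposite gaps in the two arms. Nor does the omission reach the primary outcome, since SDQ is in Table 2 at all three time points.

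The parent rows and the unnamed parent are a minor related inconsistency. They call for a clear definition rather than any claim of material bias.

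**What to change.** - Add FAD and PS to Table 2, at baseline and at each follow-up where they were collected.
- In Primary and secondary analyses and in Table 2, tie PSP, PSS and FAD to one parent identified from baseline information in every randomised family, dropouts included. The primary caregiver already used in Table 1 would serve. Use that same person's baseline as the covariate.
- If a different parent was seen at 50 months, treat the chosen parent's score as missing and impute it.
- Keep the second parent's PSP and PSS as baseline and 18-month auxiliaries only.

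Defining the outcome by whichever parent was seen at 50 months would not work. No such parent exists in the dropout families that must be imputed, and the definition would depend on an event after randomisation.

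The cost is SAP wording and data-set construction, with no new data collection. The imputation model gains a few variables, and some 50-month scores will be imputed where the informant changed.
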